BSTIM Protocol – Version 4 (December 13, 2023)

Originally proposed DSMB protocol, with statistical analysis plan moved to Statistical Analysis File.

Effect of Noninvasive Electrical Brain Stimulation on Memory Performance at Different Times of Day in Younger and Older Adults

Study Principal Investigator:

[name], Professor, Department of
Psychology University of Chicago

Supported by:

The National Institute on Aging

1R21AG060444 : BRAIN STIMULATION AND TIME OF DAY IN COGNITIVE AGING

Study Intervention Provided by:

not applicable

Sponsor of IND (IDE):

not applicable

-
-

BSTIM:

Effect of Noninvasive Electrical Brain Stimulation on Memory Performance at Different Times of Day in Younger and Older Adults

Objectives

We have recently found that tDCS has a larger impact on episodic memory in the morning, but given the mixed literature on tDCS, we aim here to (1) complete a reliable replication attempt of these published tDCS findings, (2) extend this time-of-day tDCS research in new directions, including aging, and (3) explore interesting, yet secondary, aging and memory questions within our non-tDCS (baseline data) data.

Aim 1: Determine the extent to which tDCS to left dorsolateral prefrontal cortex (or dlPFC) boosts recollection accuracy and working memory performance as a function of time-of-day in younger and older adults.

Secondary: Assess the relationship between objectively measured sleep patterns and self-reported morning-evening preferences on memory performance, and possible interactions with tDCS.

Aim 2: Determine the extent that tDCS to dlPFC boosts information-specific processes compared to information-general cognitive control processes in younger and older adults. The cognitive tasks will experimentally pit information-specific (words, pictures) and cognitive control (easy, hard) to test dlPFC tDCS effects in each age group.

Secondary: Determine the regional specificity of tDCS on task performance in younger adults, by comparing the impact of tDCS to left dlPFC and left parietal cortex (an active stimulation control site, as in Gray et al., 2015).

Aim 3: Determine the extent to which a pre-post between-subjects tDCS design can improve the detection of stimulation effects, while also preserving the validity of the sham condition.

Design and Outcomes

50 Younger Adults will be randomly assigned to three between-subjects tDCS conditions (left prefrontal, sham, left parietal control, total YA n=150) and 50 cognitively normal older adults will be randomly assigned to two between-subject tDCS conditions (left prefrontal, sham, total OA n=100). Each participant will complete 3 sessions: orientation/baseline (no tDCS, time varies), AM tDCS, PM tDCS (counterbalancing the order of the AM and PM sessions). Primary outcome measures will be cognitive task performance (episodic recollection accuracy primary, working memory accuracy secondary) as a function of 3 key factors (age group, tDCS

○

○

condition, and time-of-day) and their interaction, and also as a function of secondary factors obtained from actigraphy sleep data, sleep diary/log data, and the Morningness-Eveningness Questionnaire (aka the Owl-Lark assessment).

Interventions and Duration

Morning testing sessions will be scheduled at 8 or 9 AM, afternoon testing sessions will be scheduled at 3 or 4 PM. These times were chosen to be similar to those we used in our preliminary work that demonstrated time-of-day effects on tDCS in younger adults (9 am vs 1 pm), except we have shifted the PM session to 3 or 4 PM to be more consistent with aging studies that have found AM and PM effects on episodic memory (May & Hasher, 2017; May et al., 1993; Intons-Peterson et al., 1998)

Active tDCS will involve 20 minutes of continuous electrical stimulation (2.0 milliamperes, mA). Sham tDCS will involve 1 minute of stimulation at the start of the 20 minute period (i.e., 30 s to gradually ramp up to 2.0 mA, and then 30 s to ramp down), and also 1 minute of stimulation at the end of the 20-minute period. As in our prior work, during stimulation participants are instructed to sit quietly while remaining awake in preparation for the upcoming memory test, but no further instructions are given.

Standard Anodal Procedure. The tDCS technique that we use, modeled after the most effective techniques found in the literature (e.g., Nitsche et al., 2008), and aimed at targeting left

prefrontal cortex (for recent electrical models of tDCS, see Opitz, Paulus, Will et al. NeuroImage 2015) involves 3 basic steps: (1) the anodal electrode (35 cm²) is placed on the scalp over left dlPFC (F3 using the 10-20 EEG system, which typically centers over posterior middle frontal gyrus BA 8/9, Herwig et al, 2003), and the cathodal electrode is placed over the contralateral supraorbital site, thereby maximizing anodal stimulation of dlPFC and surrounding areas; (2) while sitting quietly, the brain is stimulated with mild electrical current (2 milliamperes, mA, using gradual ramping) for a total time of 20 minutes (stimulation condition), or a few seconds of mild current with no stimulation during most of 20 minutes (sham condition); and (3) post-stimulation cognitive task are administered, measuring performance enhancements (stimulation > sham). We have found this procedure reliably boosts recollection accuracy for at least 25 minutes post-stimulation, and in the literature, dlPFC effects on working memory have lasted at least 30 minutes post-stimulation (Ohn et al., 2008). Note that the cathodal tDCS electrode has been used to interfere with cognition, but the current project focuses on the anodal-based cognitive enhancement technique.

For tDCS, we will use a standard 1x1 tDCS Clinical Trials device (Soterix Medica, NY), specialized for double-blinding. Active stimulation will deliver 2 mA of current using 2

-
-

electrodes in 5 x 7 cm saline-dampened sponges. The anodal electrode is placed over areas F3 (left dlPFC) or P5 (left parietal) according to the 10-20 EEG-system, with the cathodal electrode on the contralateral supraorbital region. To balance the design for blinding, each of the 2 different electrode placements in the active stimulation conditions will be evenly represented in the sham condition (younger adults only). To rule out general arousal effects, participants are prompted to make an arousal rating immediately prior to tDCS and immediately following tDCS. (Our prior work found that tDCS did not affect arousal, compared to sham.)

Sample Size and Population

Younger adults – Frontal stimulation (n=50)

Younger adults – Parietal stimulation (n=50)

Younger adults – Sham (n=50; n=25 frontal placement, n=25 parietal placement)

Older adults – Frontal stimulation (n=50)

Older adults – Sham (n=50)

-
-

STUDY TEAM ROSTER

Principal Investigator: **[name]**

Department of Psychology
University of Chicago
*[name]

1 STUDY OBJECTIVES

1.1 Primary Objective

Test the extent to which tDCS to left prefrontal cortex (compared to sham) impacts different aspects of cognitive performance on different cognitive tasks as a function of age group (younger, older) and time of day (AM, PM).

1.2 Secondary Objectives

Test the extent that sleep-related measures inform the primary objectives (above), evaluate the value of including the pre-tDCS baseline cognitive measures in the analyses, evaluate the regional specificity of tDCS effects in younger adults by including a left parietal control site. Also, secondary objectives will include interesting memory and aging questions, independent of tDCS, described below.

2 BACKGROUND AND RATIONALE

2.1 Background on Condition, Disease, or Other Primary Study Focus

A better understanding of how tDCS impacts cognitive function in younger and older adults will have widespread impact. tDCS is the safest and most accessible, non-invasive brain stimulation technique available for testing causal links between different brain regions and functions, and also for attempting to improve and train cognitive abilities in older adults. By identifying key experimental factors that can improve the reliability and robustness of stimulation effects on cognitive performance in different age groups, this project should lead to the widespread adoption of these design features in future scientific and clinical applications. Moreover, we will test the extent that tDCS to dlPFC improves memory performance by boosting information-specific processes and/or cognitive control processes that operate across different types of information, thereby informing basic theories of how dlPFC contributes to memory in younger and older adults.

2.2 Study Rationale

Transcranial direct current stimulation (tDCS) to dorsolateral prefrontal cortex (dlPFC) has been shown to temporarily improve cognition in younger and older adults. Although the current spatial resolution is limited, the technique's ability to improve cognition by selectively stimulating brain regions has significant potential to advance scientific studies of human

-
-

cognition. Recently, we have discovered that time-of-day is critical for finding tDCS effects on memory in younger adults, an overlooked factor that may be responsible for mixed results in past studies. Our results also indicate that prior tDCS studies have had too few participants to reliably find the kinds of tDCS effects that we have observed (see also Minarik et al., 2016). Motivated by these discoveries, the current project uses a rigorous and well-powered approach to determine the importance of time-of-day for detecting tDCS effects on memory in younger and older adults, populations that have been targeted in many prior tDCS studies but have different optimal times-of-day. We will use the same tDCS stimulation procedures that we have used in our prior work, which were based on common tDCS parameters for cognitive studies in humans and are noninvasive, minimal risk procedures.

3 STUDY DESIGN

- Study Design: Double-blind, sham-controlled, age group x time-of-day tDCS study, with secondary analyses on sleep data, within-subjects baseline, and left parietal (younger adults only)
- Study Arms: 50 YA (active frontal), 50 YA (active parietal), 50 YA (sham: 1/2 prefrontal, 1/2 parietal), 50 OA (active frontal), 50 OA (sham: all frontal)
- Study Location: [name] Memory Lab, Department of Psychology, University of Chicago, Hyde Park Campus.
- Each participant ideally enrolled for 7 days (with flexibility up to 12 days), depending on scheduling constraints
- Intervention: 20 minutes of tDCS to prefrontal or parietal scalp locations, once during the AM (8 or 9am) and once during the PM (3 or 4 pm)
- Randomization and double-blinding separately for each age group

4 SELECTION AND ENROLLMENT OF PARTICIPANTS

Inclusion and Exclusion Criteria

Participants must meet all the inclusion criteria to participate in this study, and candidates meeting any of the exclusion criteria will be excluded from study participation:

4.1 Inclusion Criteria:

- Right-handed (according to the [Edinburgh Handedness Inventory](#))
- Normal or corrected vision
- Fluent in English (started learning by age 6)

○
○

- Ability to understand and provide informed consent for study procedures, and to comply - with study procedures for the entire length of the study.
- For individuals in the ‘younger adults’ group, must be between 18 and 30 years of age
- For individuals in the ‘older adults’ group, must be between 60 and 75 years of age
- For individuals in the ‘older adults’ group, a score of 23 or above on the Montreal Cognitive Assessment (out of 30, education-corrected) is required. This is to minimize the inclusion of suspected mild cognitive impairment (MCI) or dementia, targeting individuals that score in the normal range according to the recent meta-analysis of MoCA’s ability to differentiate normal aging from MCI in Carson et al. (2018, Int. J of Geriatric Psychiatry).
- Performance above threshold on the episodic memory task during the baseline session. The threshold is defined as having a hit rate that is at least 5% greater than the false alarm rate, where hit rate is defined as the number of studied items identified as studied, divided by the total number of studied items, and false alarm rate is defined as the number of new items identified as studied, divided by the total number of new items. We don’t anticipate this threshold to exclude many, if any subjects.

4.2 Exclusion Criteria:

- Neuropsychological conditions associated with cognitive decline or seizure
- Cochlear implants or metal in the brain/skull (except titanium)
- Psychoactive medications or psychotic diagnoses
- History of excessive use (clinically treated) alcohol or narcotics
- Hospitalization for head trauma (e.g. concussions) in the past 5 years
- Individuals above a threshold score on an assessment of depression, specifically, a score of 10 or above on the PHQ-9 (Manea et al., 2012)
- Risk of pregnancy
- Low tolerance of skin irritation
- Prior brain stimulation experience (self-report)

4.3 Study Enrollment Procedures

- Younger adults will be recruited from the University of Chicago (primarily students) and surrounding community, and older adults will be recruited from a database maintained by the [name] lab, as well as newly recruited participants from the Chicago area using word-of-mouth and advertisements (e.g., Chicago Tribune).

-
-

- Study coordinator will maintain a Screening Log including reasons for ineligibility and for non-participation of eligible candidates.
- The Study Coordinator will recruit participants, and if they are eligible and wish to participate, use AM/PM Randomization REDCap database to assign them to have their AM session first or their PM session first. The participant will then be scheduled for all 3 sessions.
- Participants will give informed consent for all 3 sessions during the baseline/study orientation day. All participants must consent for themselves. At this time they are considered enrolled.

5 STUDY INTERVENTIONS

5.1 Interventions, Administration, and Duration

Standard tDCS will be used, with 20mA of electricity for 20 minutes during the active sessions. This is a minimal risk technique, with potential adverse effects including irritation, itching, pain or discomfort under the scalp electrodes.

For tDCS administration we will use a 1x1 Transcranial Electrical Stimulation (tES) device for Clinical Trials purchased from Soterix Medical Inc. (NY, NY). The two stimulation parameters (stimulation, and sham) will be pre-programmed into the device by Soterix, using a series of codes that are provided to the PI. The PI will use these codes to develop the participant randomization scheme for each arm of the study, to achieve double-blinding (see **Section 5.2**, below). Prior to the start of the study, a random sampling of 20 of the factory-provided codes will be double-checked by the lab using a digital multimeter (500 codes will be provided by Soterix, the study will use 250).

The University of Chicago IRB ([name], Director, SBS IRB) and the PI have determined that this NIH clinical trial is classified as a basic research study under FDA guidelines, and thus this study does not require FDA approval. The manufacturer of the tDCS device, Soterix, has an Abbreviated IDE for the device, but the current study will use the device for research purposes only and with minimal (nonsignificant) risk procedures that do not require FDA approval.

5.2 Handling of Study Interventions

The Study Coordinator will be responsible for collecting a large portion of the data, and they will not be privy to the stimulation/sham assignments of each participant. Instead, they will only be given access to a soterix stimulation code determined for each participant ahead of time to be inputted into the tDCS device at the time of testing. This code will be linked to

-
-

either a sham or stimulation testing session, ensuring complete double-blinding regardless of the experimenter.

Double-blinding. All participants are informed that they will receive tDCS brain stimulation during the 20 m session, with different amounts of electricity and timing depending on the experimental condition, and also that the typical sensation of tingling or itchiness might habituate. This accurately describes the sensations in the sham condition, because stimulation is briefly presented, as well as the sensations in the stimulation condition, as participants do often habituate.

Soterix Medical Inc. will create codes in advance for the tDCS device, which, when entered into the device, will deliver either active or sham stimulation. A subject will be randomly assigned to a code just before the first stimulation session, using REDCap's randomization feature. None of the the study personnel will have access to the spreadsheet that links the codes to the active or sham condition. [name] and [name] will have access to this spreadsheet, and will complete the randomization setup in the REDCap databases.

5.3 Concomitant Interventions

See inclusion/exclusion criteria.

5.4 Adherence Assessment

Adherence to the study regimen is defined as participants completing all 3 testing sessions and returning the actigraphy watch. Primary analyses will include data only from participants completing all 3 sessions.

-
-

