6.2.2 Enrollment, Baseline, and/or Randomization

Enrollment & Randomization

Enrollment begins when the participant signs the informed consent form for the 3-session experiment, at the start of the first lab session (i.e., baseline/orientation day).

-
-

After successful screening, participants will be randomized to either the AM-session-first condition or to the PM-session-first condition using the AM/PM Randomization REDCap database. Just prior to the baseline session, the participant will be assigned to a cognitive task condition using the Task Condition Randomization REDCap database. Finally, just before the first tDCS session, the participant will be assigned to a Soterix stimulation code, and to an electrode placement (either PFC or parietal), using the Participation REDCap database.

Baseline Assessments

During baseline assessment participants will complete cognitive tasks, demographic information, and other forms (Table 6.1).

[Morningness-Eveningness Questionnaire](#) (MEQ) *online survey* - Participants will take the MEQ, assessing AM and PM testing preferences, which is correlated with physiological measures of circadian rhythms and predicts time-of-day effects on cognitive tasks in younger and older adults (Horne & Ostberg, 1976; see May & Hasher, 2017). Younger adults are expected to express at least a mild preference for PM testing (approximately 70% of younger adults in our prior sample), and older adults at least a mild preference for AM testing (typically 75% of older adults, see Yoon et al., 1999). (See Appendix).

[Actigraphy and Sleep Diary](#) *online survey* - During the initial orientation session participants will be equipped with an actigraphy watch and instructions for this and the sleep diary, and these data will be collected over a minimum 7-day period. During this period, participants will return to the lab for 2 testing sessions (AM/PM, nonconsecutively), returning the actigraphy watch and sleep diary on the final testing session. These measures will be used to help interpret the differential time of day effects (AM vs PM) on cognitive functions that we predict in younger and older adults, as well as the predicted interaction with tDCS brain stimulation.

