The debriefing sheet also will include citations for further reading. (See Appendix). *About Early Termination:* Participants have the right to end their participation at any time. In addition, the PI may terminate participation if a participant is in obvious non-compliance with the study procedures (e.g., responding randomly or sleeping during the cognitive task) or shows signs of moderate or severe adverse events associated with the study procedures (e.g., excessive discomfort with the tDCS electrodes).

-
-

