8 INTERVENTION DISCONTINUATION

Participants may withdraw voluntarily from participation in the study at any time and for any reason. Because the adverse events associated with tDCS are mild and transient, we will not continue to follow participants that withdraw from the study. Participants reporting headache will be given the option to rest in the lab until the situation resolves.

Data from participants that discontinue without completing both experimental testing sessions will be replaced with a new participant assigned to the same condition.

In the event that participation in the study is halted during or following tDCS, the participant will be asked to complete the Post-tDCS Application Survey and also will receive debriefing.

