Power analysis: Our power analysis was based on our most recent and largest tDCS experiment with younger adults (Wong et al., in press, $n = 30$ per each between-subjects condition), which yielded a 12% difference in word test accuracy between sham (.23, $SD = .21$) and active tDCS (.35, $SD = .21$) in the 9 AM group, predicting that we would need 50 participants in each stimulation group in order to obtain a similar effect size (Cohen's $d = .57$, or a medium effect size) with 80% power at $p < .05$ (2 tailed, calculated with G-Power, v. 3.1.9.3). We therefore plan to test 50 younger adults and 50 older adults in each stimulation condition in order to detect effects of this magnitude. These sample sizes are considerably larger than most (if not all) of the between-subjects tDCS experiments on episodic memory published as of 2017. A sample size of 50 per condition also should yield sufficient power to detect the 2x2 interaction between brain stimulation (between-subjects) and time-of-day (within-subjects) in each age group, if we assume a similar effect size (partial eta squared = .06) for the interaction between time-of-day and stimulation we had obtained in younger adults in Wong et al. (in press), and also a .25 correlation between the repeated measures during AM and PM (80% power, alpha = .05).

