## Analysis Plan

### PRIMARY ANALYSES

Set 1 (1a, 1b, 1c). The first set of primary analyses will estimate the effect of tDCS to left dlPFC on cognitive performance and the extent to which different aspects of the cognitive task will be impacted. These analyses will be done separately for episodic and working memory.

1.a This analysis will be done on younger adults only. We shall use a linear mixed (i.e., random participant-level intercepts) model with memory performance (defined as memory accuracy computed by subtracting false alarms from target hits) as the dependent variable and stimulation condition (stimulation vs. sham), session Time of Day (AM, PM), and task manipulations (stimulus format and difficulty) as within-subjects predictors along with session order as a covariate (session 1, session 2). Interaction terms between stimulation condition and both task manipulation and time of day will be used to examine the impact of these variables on the stimulation effect.

1.b This analysis will use the same model as in 1a (above), but including data from both younger and older adults and a corresponding age-group factor in the model. Interaction terms between age group, stimulation condition, and time-of-day will be used to determine whether the overall stimulation effect is the same for older as for younger adults, and if not, whether the difference varies by time of day.

1.c This analysis will assess the impact of preferred time of day on tDCS effects, using wrist-worn (minimum 7-days, max 12-days) accelerometry to measure preferred time of day (i.e. “Owl” vs “Lark”), and validation using the subjective Morningness-Eveningness Questionnaire (MEQ). For this analysis, accelerometry-derived variables capturing preferred time of days (eg, including wake time, rise time and midpoint of sleep) will be added as covariates to the model in 1.b., and interactions between these, time of day and stimulation effects will be evaluated.

Set 2. The second set of primary analyses will focus on dlPFC vs parietal vs sham effects in younger adults only. For these analyses, similar models to those described above will be used (e.g., 1a, 1c, 2), except we will include 3 levels for tDCS (dlPFC, parietal, sham). We will test the relative fit of three models: (1) a model in which parietal has the same effect as sham, (2) a model in which parietal has the same effect as dlPFC, and (3) a model in which the effect of parietal differs from the other two conditions.

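### Protocol 5.4 drops randomised participants who have outcome data from only one tDCS/sham session, although the SAP mixed model can use those data; the likely effect is small and the fix is short

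*Protocol*

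**What the plan says.** Protocol 5.4 sets the analysis population: "Primary analyses will include data only from participants completing all 3 sessions". Protocol 8 adds: "Data from participants that discontinue without completing both experimental testing sessions will be replaced with a new participant assigned to the same condition".

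Arm assignment comes late. Protocol 5.2 says: "A subject will be randomly assigned to a code just before the first stimulation session". Protocol 6.2.2 agrees: "just before the first tDCS session, the participant will be assigned to a Soterix stimulation code". Accuracy is measured at baseline and in each tDCS session (Protocol 9.4.1).

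SAP Primary Analyses 1.a specifies a "linear mixed (i.e., random participant-level intercepts) model", extended in 1.b, 1.c and Set 2. The SAP first runs every analysis without the baseline score and then repeats it with baseline adjustment. The SAP text available for this review names no analysis set and no method for missing sessions, so the point rests on the explicit rule in Protocol 5.4.

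**The concern.** A participant who finishes one tDCS/sham session and misses the other has an outcome under a randomly assigned arm. Excluding that outcome and substituting a new participant restores the count but not the randomised comparison.

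Some exits are tied to the procedure or to performance. Participation can cease when sensations become intolerable (Protocol 7). An unresolved adverse event possibly related to the procedures halts it (7.5). Under early termination (6.2.4), "the PI may terminate participation if a participant is in obvious non-compliance with the study procedures". Protocol 9.1 also notes that stimulation and sham produce different sensations on average. Loss may therefore differ by arm.

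The overall stimulation contrast is what is at stake. The SAP tests further only if the coarsest-level test is significant, so a shift there can carry forward. Participants lost before code assignment have no arm and no tDCS outcome, and are not part of this point.

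**Working it through.** **1. The plan's own figure.** Protocol 9.2 gives means of .23 and .35 with SD .21, so d = .12/.21 = .571. At 80% power and two-sided .05, a t-test needs 50 per group (power .806 at d = .57); the normal approximation gives 49. The stated 50 reproduces. Because leavers are replaced, 50 completers per arm and the planned power are kept. The issue is selection, not sample size.

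**2. Inputs.** From Protocol 9.2: SD .21, AM/PM correlation .25, 50 per arm. Assumed, because the documents give no dropout rate: loss proportions p after code assignment, and D, the number of SDs by which leavers score lower. The calculation uses one score per session.

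**3. Shift in the overall effect, completers only** = (p_active − p_sham) × D.

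| Loss, active v sham | D = 0.5 | D = 1 |
|---|---|---|
| Equal, similar leavers | 0 | 0 |
| 5% v 1% | .04 × .5 = .02 | .04 |
| 8% v 2% | .06 × .5 = .03 | .06 |
| 10% v 2% | .08 × .5 = .04 | .08 |

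The top value is .08/.57 = 14% of the planned effect, or .08 × .21 = .017 in accuracy. The standard error is sqrt(2/50) = .200 for the AM contrast and sqrt(2 × .625/50) = .158 for the AM+PM mean, so .08 is 0.40 and 0.51 of a standard error.

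**4. How much of the shift is removed by keeping one-session data.** The mean of two sessions has variance (1 + .25)/2 = .625 against 1 for a single session, so a one-session participant has weight w = .625. With h the share of leavers who have an outcome, the effective leaver share is g = whp/(whp + 1 − p). For 10% v 2%:

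- All leavers have an outcome (h = 1): .0625/.9625 − .0125/.9925 = .0649 − .0126 = .0523. Removed: .0523/.08 = 65%; at D = 1, .08 falls to .028.
- Half do in both arms (h = .5): .0336 − .0063 = .0272 (from unrounded values). Removed: 34%; .08 falls to .053.
- The excess active losses stop during the first stimulation, so only 2 of the 10 points have an outcome, against 2 of 2 in sham: .0125/.9125 − .0125/.9925 = .0137 − .0126 = .0011. Removed: about 1%; .08 falls only to .079.

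At 5% v 1% the first two cases give 64% and 33%.

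**5. Variance.** Hold 50 completers per arm and add m = 50p/(1 − p) one-session participants, half AM and half PM: m = 2.63 at 5% and 5.56 at 10%.

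- Overall effect: (m/2)/(40 + m/2) = 3.2% and 6.5%.
- Stimulation by time of day: (m/2)/(66.67 + m/2) = 1.9% and 4.0%.
- If half the leavers have no outcome: 1.6% and 3.4% overall, 1.0% and 2.0% for the interaction.

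**6. Simulation check** (20,000 trials, 50 completers per arm, 10% v 2%, Monte Carlo SE .001). The completers-only shift was .039 at D = .5 and .079 at D = 1. With one-session data kept it was .014 and .028 (h = 1), or .027 and .053 (h = .5). The interaction shift stayed within .0022 of zero (Monte Carlo SE .0017) with D equal in both sessions.

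**The case against.** The strongest case against has four parts.

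- **The size is assumed, and its top is hard to support.** Protocol 7.1 reports similar adverse-effect frequencies in active and sham, with a largest gap of 6 points (itching). An 8-point gap in leaving would exceed the largest gap in having any listed symptom. Those are review figures rather than dropout rates, but they make .08 SD unlikely. The eligibility rule "Performance above threshold on the episodic memory task during the baseline session" also removes near-chance performers before a code is assigned. This stands, and so does its consequence: the shift may be near zero.
- **Keeping the data may recover little.** The tasks follow stimulation, so someone who stops during the first stimulation has no outcome. Step 4 shows recovery of about 1% when the excess losses are of that kind. This stands. By contrast, exits for adverse events may carry an outcome, because Protocol 7.3 asks about events after the tasks.
- **Analysis 1.c needs more than an outcome.** It calls for at least 7 days of accelerometry. Sessions may be 48 hours apart, and 7 days is assured only by the final session (Protocol 6.2.3), so a one-session leaver may lack it. This stands, and the fix must allow for it.
- **Completers are a defensible set in a mechanistic study.** Retaining leavers admits sessions ended for sleeping or random responding. This is a real cost, but a completers-only sensitivity analysis meets it. A pre-specified set is still better defined by assignment than by what happens afterwards.

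**Conclusion.** The rule should be changed, but the likely effect is small. On the assumed losses the overall stimulation effect shifts by 0 to 0.08 SD, at most about half a standard error, and the upper end is unlikely. Retaining one-session data removes about 1% to 65% of any shift, under a constant deficit D and depending on how many leavers produced an outcome. The gain in variance is 3.2% to 6.5% for the overall effect and 1.9% to 4.0% for the interaction at 5% to 10% loss, and about half that if half the leavers have no outcome.

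A reader might infer more than the documents support:

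- *That the tDCS effect will be inflated.* No dropout rate or arm difference is given, and equal losses of similar participants give no shift.
- *That the trial loses power.* Protocol 8 replaces leavers, so 50 completers per arm remain.
- *That the time-of-day interaction is biased.* It does not shift if leavers score equally lower in both sessions. Protocol 9.2 claims "sufficient power to detect the 2x2 interaction between brain stimulation (between-subjects) and time-of-day (within-subjects) in each age group", and this point does not disturb that claim.
- *That replacing within the same condition breaks the blind.* Protocol 5.2 and 10.1 describe keyholders who set up the randomisation, and 5.1 shows spare codes. Nothing there implies unblinding.

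**What to change.** Replace the Protocol 5.4 sentence with:

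> The primary analysis set is every participant assigned a stimulation code who has outcome data from at least one tDCS/sham session, analysed in the assigned arm with the SAP mixed model; analysis 1.c uses those in this set who also have the required accelerometry (minimum 7 days). A completers-only analysis is a sensitivity analysis. Losses after code assignment, including participants with no outcome, are reported by arm with reasons and timing (before or after the first outcome).

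In Protocol 8, state that a replacement is added to, and does not displace, the data of the participant who left. Keep enrolment and the code-break trigger in Protocol 9.2.1 counted on three-session completers, so that 50 per arm and the planned interaction power are preserved. Repeat the analysis-set sentence in the SAP. Any Set 2 model that carries the 1.c covariates needs the same accelerometry condition.

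The cost is a few sentences in the protocol and one in the SAP, with no new data and no change to enrolment. Two downsides remain. Sessions ended for random responding or sleeping enter the primary set, which the completers-only analysis addresses. Bias from leavers with no outcome is not removed, which is why losses should be reported by arm and timing.
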